7.4. Schedule of Visits

The schedule of visits, including timelines for clinical documentation, clinical scoring, patient questionnaires, and imaging procedures, is outlined in Table 1. All procedures listed in Table 1 represent standard clinical assessments routinely performed in the care of patients with atopic dermatitis. The Genital-Investigator Global Assessment (g-IGA) is a scale used to evaluate the severity of genital skin inflammation in affected patients. Assessment of skin changes using non-invasive imaging techniques (OCT, confocal microscopy, or LC-OCT) will be performed, where feasible and acceptable to participants. OCT is a non-invasive, non-injurious imaging modality that is safe for patients and is frequently employed in routine dermatological care. Imaging will be conducted at both centers. Image analysis will be carried out at the Department of Dermatology, UKA, Augsburg, Germany.

Table 1: Schedule of visits, clinical documentation, clinical scores, patient questionnaires, and imaging.

Visit	1	2	3	4	5
Week	0	4	16	24	52
Procedure:					
Informed consent	X				
Confirmation of eligibility	X				
Patient demographics	X				
Medical history, prior and concomitant therapies as well as surgeries	X				
Weight, Height, body mass index (BMI)	X				
Genital-Investigator Global Assessment (g-IGA)	X	X	X	X	X
Eczema Area and Severity Index (EASI)	X	X	X	X	X
Investigator Global Assessment (IGA)	X	X	X	X	X
SCORing Atopic Dermatitis (SCORAD)	X	X	X	X	X
Localized SCORing Atopic Dermatitis (I-SCORAD)	X	X	X	X	X
Genital-Numeric Rating Scale (g-NRS)	X	X	X	X	X
Sexuality Questionnaire Lindenmeyer	X	X	X	X	X
Sexual Behavior Questionnaire (SBQ-G)	X	X	X	X	X
Dermatology Life Quality Index (DLQI)	X	X	X	X	X
Patient-Oriented Eczema Measure (POEM)	X	X	X	X	X
Atopic Dermatitis Control Tool (ADCT)	X	X	X	X	X
Hospital Anxiety and Depression Scale (HADS)	X		X		X
Non-invasive imaging*	X	X	X	X	X

*Exploratory assessment of skin changes using non-invasive imaging techniques (OCT, confocal microscopy, or LC-OCT) will be performed, where feasible and acceptable to participants. Imaging will be conducted at both centers. Image analysis will be carried out at the Department of Dermatology, UKA, Augsburg, Germany.

7.4.1. Clinical, demographic and imaging assessments

The following assessments will be conducted during the study. Items 1 to 5 focus on gathering general patient information. Clinical signs will be assessed using the g-IGA, EASI, IGA, SCORAD and I-SCORAD for the genital area. Symptoms will be evaluated with the Genital-NRS. Quality of life will be assessed using the Sexuality Questionnaire Lindenmeyer, SBQ-G, DLQI, POEM, ADCT, and HADS.

7.4.2. Clinical documentation and safety

Clinical Documentation & Safety will be asked at first visit on week 0 and until week 52 depending on the item. Data is consisting of:

- Date of birth / age
- Gender
- Medical/Surgical history and previous medications
- Adverse Events / SAEs
- Concomitant therapy
- Initial diagnosis of AD
- AD treatment history

- Weight
- Height

Patients' height will be measured and documented in the beginning, the weight throughout the study. The body mass index (BMI) will be calculated using the formula.

$$BMI = (\text{weight in kilograms} / (\text{height in meters} \times \text{height in meters})).$$

7.4.3. Scores Assessing Clinical Signs

The following scores will be recorded at baseline and at each scheduled follow-up visit throughout the study.

Genital-Investigator Global Assessment (g-IGA)

The g-IGA is a clinician-reported tool used to assess the severity of genital involvement in AD, as previously described (9). It utilizes a 5-point scale developed, incorporating morphological criteria:

- **0 – Clear:** No signs of inflammation (e.g., erythema, induration, lichenification, oozing, or crusting). Postinflammatory hyper-/hypopigmentation may be present.
- **1 – Almost Clear:** Minimal erythema and slight induration or lichenification; no oozing or crusting.
- **2 – Mild:** Mild erythema (pink), slight induration or lichenification; no oozing or crusting.
- **3 – Moderate:** Noticeable erythema (dull red), induration, or lichenification; oozing/crusting may occur.
- **4 – Severe:** Marked erythema (bright/deep red), pronounced thickening, and/or widespread lesions; oozing or crusting may be present.

Eczema Area and Severity Index (EASI)

The EASI is used to assess the severity and extent of signs of AD in patients. It evaluates four key parameters: Erythema, infiltration, excoriation, and lichenification, each rated on a scale of 0 to 3 (0 = none, 3 = severe). These parameters are assessed across four body regions: Head/neck, upper limbs, trunk, and lower limbs.

The total EASI score is calculated by combining the severity of the four parameters with the affected body surface area (BSA) (expressed as a percentage of the total body surface area). The resulting score ranges from 0 to 72, with higher scores indicating more severe eczema.

Investigator's Global Assessment (IGA)

The IGA is a clinician-assessed scale used to evaluate the overall severity of AD. The IGA is based on a visual inspection of the patient's skin and is rated on a 5-point scale:

0 = Clear (no signs of AD)

1 = Almost Clear (few residual lesions)

2 = Mild (slight redness, itching, and/or scaling)

3 = Moderate (moderate redness, itching, and/or scaling)

4 = Severe (intense redness, itching, scaling, and/or thickened skin)

SCORing Atopic Dermatitis (SCORAD)

The SCORAD is a validated clinical tool used to assess the extent and severity of AD. It integrates both objective clinical signs and patient-reported symptoms into a composite score ranging from 0 to 103. The extent of the disease is calculated using the "rule of nines" to estimate the percentage of body surface area affected. Intensity is assessed based on six clinical signs: erythema, edema/papulation, excoriation, lichenification, oozing/crusts, and dryness, each scored on a 4-point scale: 0 = none, 1 = mild, 2 = moderate, and 3 = severe. Subjective symptoms, specifically pruritus and sleep disturbance, are recorded by the patient using visual analogue scales ranging from 0 to 10.

Localized SCORAD for the Genital Area (I-SCORAD)

The I-SCORAD is an adapted version of the SCORAD designed to evaluate the severity of AD in the genital area. This tool focuses solely on the intensity of skin lesions within the localized site and excludes overall body surface area and patient-reported symptoms. The same six clinical signs (erythema, edema/papulation, excoriation, lichenification, oozing/crusts, and dryness) are assessed and scored on a 4-point scale (0 = none, 1 = mild, 2 = moderate, 3 = severe).

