Further studies with larger patient populations are warranted to confirm these findings, assess long-term clinical benefits, and investigate the corresponding improvements in patient-reported outcomes.

2. Study Purpose

This study aims to investigate improvements in genital PROs in patients with moderate-to-severe AD involving the genital region during treatment with tralokinumab in routine clinical care over a 52-week period. Additionally, the study will assess changes in both local (genital-specific) and general clinical scoring systems, as well as evaluate skin changes using non-invasive imaging techniques such as confocal microscopy, optical coherence tomography (OCT), or line-field optical coherence tomography (LC-OCT).

3. Study Objectives

Primary Endpoint	Improvement of $\geq 50\%$ in Genital-Numerical Rating Scale (g-NRS) or ≥ 2 points in Genital-Investigator Global Assessment (g-IGA) in patients with moderate-to-severe AD treated with tralokinumab over a 52-week period.
Secondary Endpoints	Improvement in general PRO instruments [e.g., Patient-Oriented Eczema Measure (POEM), Atopic Dermatitis Control Tool (ADCT), Dermatology Life Quality Index (DLQI), Hospital Anxiety and Depression Scale (HADS)] in patients with moderate-to-severe AD undergoing treatment with tralokinumab over a 52-week period.
	Improvement in overall disease severity [e.g., Eczema Area and Severity Index (EASI), SCORing Atopic Dermatitis (SCORAD), Investigator Global Assessment (IGA)] in patients with moderate-to-severe AD undergoing treatment with tralokinumab over a 52-week period.
	Exploratory assessment of skin changes using non-invasive imaging techniques (OCT, confocal microscopy, or LC-OCT) will be performed, where feasible and acceptable to participants, in patients with moderate-to-severe AD receiving tralokinumab over a 52-week period. Imaging will be conducted at both centers. Image analysis will be carried out at the Department of Dermatology, University Hospital Augsburg (UKA), Augsburg, Germany.

4. Study Design

This is a prospective, open-label, exploratory, non-randomized, non-blinded study. A total of 30 patients diagnosed with moderate-to-severe AD involving the genital region will be treated with tralokinumab as part of routine clinical care, in accordance with the Summary of Product Characteristics for tralokinumab, over a 52-week period.

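### The IGA is described as a visual score of signs, but its anchors for grades 2 to 4 list itching, so read literally the grades overlap

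*Protocol*

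**What the plan says.** Section 7.4.3 of the Protocol covers scores of clinical signs. It introduces the IGA with "The IGA is a clinician-assessed scale used to evaluate the overall severity of AD" and continues "The IGA is based on a visual inspection of the patient's skin and is rated on a 5-point scale". The lower anchors are "0 = Clear (no signs of AD" and "1 = Almost Clear (few residual lesions". The next two are "2 = Mild (slight redness, itching, and/or scaling" and "3 = Moderate (moderate redness, itching, and/or scaling". Grade 4 follows the same pattern at the highest intensity: itching is listed again, thickening of the skin is added, and the items are again joined by *and/or*.

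Section 7.4.1 also places the IGA with the measures of clinical signs and assigns symptoms to the genital NRS. Section 3 gives the IGA its endpoint role, as one of three examples under a secondary endpoint: "Improvement in overall disease severity [e.g., Eczema Area and Severity Index (EASI), SCORing Atopic Dermatitis (SCORAD), Investigator Global Assessment (IGA". Section 10 plans to analyse change in these scores by methods similar to those for the primary endpoint, that is, paired t-test or Wilcoxon signed-rank test, with longitudinal models as an option.

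**The concern.** The description and the anchors give the assessor two different instructions. The description says to grade what can be seen. Three of the five anchors name a symptom that cannot be seen and has to be asked about. Because the items are joined by *and/or*, any one of them is literally enough for the grade.

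Two things are at stake. The first is reproducibility: an assessor who follows the description and one who follows the anchors could reach different grades for the same patient, between the two centres or between visits of one patient. The second is interpretation: the study is open-label with a single group (section 4), so itch reported to an unblinded assessor could move a grade that the report would present as a visual finding. Neither problem can be repaired in the analysis, because a recorded grade does not show how much of it came from itch.

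**Working it through.** The plan states no figure on this point, so the check sets the texts side by side.

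**Step 1. What each IGA anchor uses (section 7.4.3).**

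| Grade | Visible signs or lesions | Itching listed | Items joined by *and/or* |
|---|---|---|---|
| 0 | yes (absence of signs) | no | no |
| 1 | yes (residual lesions) | no | no |
| 2 | redness, scaling | yes | yes |
| 3 | redness, scaling | yes | yes |
| 4 | redness, scaling, thickening | yes | yes |

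**Step 2. Whether the Protocol treats itch as visible.** It does not. In the SCORAD description (section 7.4.3), pruritus is a subjective symptom that the patient records on a visual analogue scale. POEM and ADCT (section 7.4.4) put itching to the patient as a question. Excoriation, which is a visible trace of itch, is a parameter of the EASI, but the IGA anchors say itching and not excoriation.

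**Step 3. Whether the grades exclude one another.** Two cases, read literally:

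- Few residual lesions and moderate itch: grade 1 by lesions, grade 3 by itch. Difference: 3 − 1 = 2 grades.
- No visible signs and slight itch: grade 0 by signs, grade 2 by itch. Difference: 2 − 0 = 2 grades.

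This assumes that the intensity word in each anchor applies to every item in the list. If it applied to redness only, itching of any degree would meet grades 2, 3 and 4 alike, and the overlap would be wider. No tie-break is given.

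**Step 4. Whether another part of the Protocol resolves it.** Section 10 calls every score except the g-IGA standardized and validated. Section 7.4.3, however, cites no source for the IGA and prints its own anchors, so those are what an assessor has in hand. Two neighbouring scores show that the Protocol can keep itch out when it means to: the g-IGA anchors are morphological and omit it, and the localized SCORAD expressly leaves out patient-reported symptoms.

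**Step 5. What depends on the IGA.** The primary endpoint uses the g-NRS or the g-IGA (section 3). The treatment-failure rule uses the EASI (section 9). The inclusion criteria set no IGA threshold (section 5.1). The EASI parameters are all signs. Only the secondary disease-severity endpoint is touched, through one of its three example measures.

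**Step 6. Size per patient.** With all 30 patients analysed, one patient graded 2 grades apart at only one of the two compared visits moves the mean IGA change by 2/30 = 0.07 grade. If the same reading is used at both visits and itch sets the grade at both or neither, the inconsistency between readings adds nothing. The Protocol does not say how many patients would be concerned, so no total can be given.

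**The case against.** The best defence is that context settles the matter. The section heading, the grouping in section 7.4.1 and the visual-inspection sentence all tell the assessor to grade what is seen, and the anchors are short descriptors for a global clinical judgement. A sensible dermatologist would hardly give grade 3 to almost clear skin because of reported itch. This has force: it means that assessors *could* grade differently, not that they will. It does not remove the conflict, since the anchors are part of the same instruction and say otherwise.

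Three stronger readings are tempting, and the Protocol does not support them.

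- A reader might infer that agreement between the severity endpoint and the PRO endpoint is built in by this wording. No section says that the two must be kept apart, and SCORAD, an openly composite score in the same severity endpoint, includes patient-rated pruritus by design. Correcting the IGA would not remove that overlap.
- A reader might guess a number of discordant patients and convert it into a shift in an IGA response rate. The Protocol defines no IGA response rate or threshold and gives no frequency of itch out of step with signs, so such a figure would rest on the guess alone.
- A reader might carry the problem over to the primary endpoint because the names are alike. The g-IGA has its own anchors, without itch.

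It may also be said that editing the anchors by hand creates one more unsourced version of the scale. That is fair, and it bears on how the correction is made.

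**Conclusion.** The contradiction is real and lies within one short description in section 7.4.3: a score said to rest on inspection has three anchors that include an item inspection cannot show. Taken literally, the grades are not mutually exclusive, and a single patient can fit two grades that lie 2 apart. That follows from the wording and needs no assumption about the data beyond the reading of the intensity words given above.

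The consequence is limited. One named example measure of a secondary endpoint, in an exploratory study of 30 patients, has an ambiguous scoring rule. Neither the frequency nor the direction of any effect on the results can be derived from the Protocol. Itch counted at follow-up would make improvement look smaller; itch counted at baseline only would make it look larger. It still deserves correction, because it is a scoring rule that must be settled before data are collected and cannot be left to the analysis plan.

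**What to change.** Before the first patient is graded, make the IGA anchors in section 7.4.3 and on the CRF agree with the visual-inspection sentence, in one of two ways:

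- remove itching from grades 2, 3 and 4, leaving redness, scaling and thickening; or
- print the sign-only anchors of a named and cited IGA version.

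Leave itch to POEM, ADCT and the SCORAD pruritus scale, all scheduled at each of the five visits in Table 1, so nothing is lost. Brief the assessors at both centres on the same text.

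The cost is a change of wording in three anchors and on the CRF, with no new data and no extra visit. The small downside is that the printed scale changes, so the Protocol must state which IGA version is used if the validation statement in section 10 is to stand. The second option answers that more directly than the first.

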7.4.4. Scores Assessing Symptoms

The following scores will be recorded at baseline and at each scheduled follow-up visit throughout the study.

Genital-Numeric Rating Scale (Genital-NRS)

The Genital Numeric Rating Scale (g-NRS) is a patient-reported measure that subjectively assesses the severity of genital involvement in AD on a scale from 0 to 10, as previously described (9).

Patient-Oriented Eczema Measure (POEM)

The POEM is a questionnaire designed to evaluate the symptoms of AD over the past week. It consists of seven questions addressing symptoms such as itching, sleep disturbance, bleeding, oozing, skin cracks, scaling, and dryness. For each question, the patient indicates the number of days in the past week they experienced the symptom (0 to 7 days). Each response is scored from 0 to 4 (0 = no days, 4 = every day), and the total score is the sum of these individual scores. The total score ranges from 0 to 28, with higher scores reflecting a greater symptom burden and more severe disease.

Atopic Dermatitis Control Tool (ADCT)

The ADCT is a patient-reported measure to assess the control of AD symptoms over the past week. It includes six questions on itching, sleep disturbance, daily activities, and emotional impact, with responses scored from 0 to 4 (0 = no symptoms, 4 = extreme symptoms). The total score, ranging from 0 to 24, indicates the level of control. A score of 7 or higher, or an increase of 5 points or more since the last assessment, suggests poor disease control.

7.4.5. Scores Assessing Quality of Life of Patients

The following scores will be recorded at baseline and at each scheduled follow-up visit throughout the study, except for the HADS, which will be assessed at Visits 1, 3, and 5 only.

Sexuality Questionnaire Lindenmeyer

The Sexuality Questionnaire Lindenmeyer is designed to assess various aspects of an individual's sexual health and well-being. It includes questions about the respondent's relationship status, satisfaction with their partnership, and the frequency of sexual contact. It also explores the individual's sexual behaviour, including their satisfaction with sexual activity and whether they use contraception. The questionnaire addresses any perceived sexual problems, including whether these issues may be related to alcohol or drug use. Finally, it asks whether the individual has sought medical or psychological treatment for sexual difficulties in the past and whether they currently wish for help in managing these issues. Through a combination of multiple-choice and open-ended questions, the questionnaire collects information to better understand the respondent's sexual health and identify areas where therapeutic support may be needed.

Sexual Behaviour Questionnaire SBQ-G

The SBQ-G is a standardized tool used to assess sexual function and satisfaction over the past three months. It includes questions on various aspects of sexuality, such as sexual desire, frequency of sex and masturbation, arousal, enjoyment, and overall satisfaction. Additionally, it addresses specific sexual problems like erectile dysfunction in men, premature or delayed ejaculation, orgasm ability in women, and pain during intercourse. For men, the questionnaire also includes questions about the ability to achieve and maintain an erection, as well as satisfaction with orgasm. For women, it covers orgasm frequency and satisfaction, pain during sex, and menstrual regularity. Responses are scored on a scale from 0 to 3, and a Mean Global Index of Sexual Dysfunction (MGISD) is calculated by summing specific items and computing a weighted average. Higher scores indicate greater sexual dysfunction.

Dermatology Life Quality Index (DLQI)

The DLQI is a patient-administered, ten-question, quality of life questionnaire that covers six domains including symptoms and feelings, daily activities, leisure, work and school, personal relationships and treatment (10). The DLQI has a one-week recall period.

Response categories include:

not relevant = score of 0

not at all = score of 0

a little = score of 1

a lot = score of 2

very much = score of 3

The DLQI will be self-administered by the patient at visits indicated in the activity schedule.

The DLQI will be analyzed under six headings (10 questions) as follows:

Table 2: Analysis of DLQI.

Domain	Question number	Score
Symptoms and feelings	Question 1 and 2	Score maximum 6
Daily activities	Question 3 and 4	Score maximum 6
Leisure	Question 5 and 6	Score maximum 6
Work and school	Question 7	Score maximum 3
Personal relationships	Question 8 and 9	Score maximum 6
Treatment	Question 10	Score maximum 3

Hospital Anxiety and Depression Scale (HADS)

The HADS is a self-report tool designed to assess the levels of anxiety and depression experienced over the past week. Participants are asked to select a score between 0 and 3 for

each statement. The scale includes questions related to feelings of tension, enjoyment, restlessness, and panic. Based on the total scores, the results are interpreted as follows: A score between 0 and 7 indicates normal levels, 8 to 10 suggests borderline abnormal levels, and a score between 11 and 21 indicates abnormal levels, which may require further evaluation. This tool helps to identify individuals who may be experiencing anxiety or depression, aiding in the decision for further assessment or intervention.

7.4.6. Imaging

Assessment of skin changes using non-invasive imaging techniques (OCT, confocal microscopy, or LC-OCT) have become an optional routine analysis of inflammatory skin diseases and will be performed on an availability-dependent basis. These assessments will be conducted depending on patient willingness and availability at the respective visits. Confocal microscopy, OCT, and LC-OCT will be performed at the Department of Dermatology, University Hospital Augsburg (UKA), Germany. OCT will also be conducted at the Institute and CCIM, University Hospital Schleswig-Holstein (UKSH), Lübeck, Germany.

All imaging data will be analyzed at the Department of Dermatology in Augsburg. To facilitate this, anonymized image data will be securely transferred to Augsburg on encrypted storage devices for extraction and analysis.

Confocal microscopy

Confocal microscopy is a high-resolution imaging technique, allowing non-invasive examination of skin, mucosa, hair, and nails (11). In dermatology, confocal microscopy is effective for identifying various cutaneous infections and infestations, as well as for monitoring treatment progress (12).

OCT Imaging

The VivoSight OCT System (Michelson Diagnostics Ltd, Kent, UK) will be utilized in this study. According to the manufacturer's specifications, the laser product is laser class 1 and eye safe meaning that safety goggles are not required. The emission wavelength is 1.305 nm. The optical resolution is <7.5 µm lateral and <5 µm axial. The scan area is 6 mm x 6 mm. The penetration depth is about 1-2 mm. Images will be acquired as vertical B-scans and en-face scans. The images will be saved as TIFF, TIFF stack, and DICOM formats. OCT scans will be obtained of a non-lesional skin site and a lesional skin site at investigators and subjects discretion:

- The non-lesional skin site will be at the left or right volar forearm. The same skin site will be used for all evaluations throughout the study. A body map will be used for reference so that the location is used consistently for all subsequent evaluations.

- The AD lesional skin site will be at predilection site e.g. at the elbow. The same skin site will be used for all evaluations throughout the study. A body map will be used for reference so that the location is used consistently for all subsequent evaluations.

LC-OCT Imaging

The LC-OCT is a non-invasive imaging technique that combines the depth penetration of OCT with the high lateral resolution of confocal microscopy, allowing for real-time, high-resolution visualization of skin architecture in both cross-sectional and en-face modes.

8. Data Handling

During the study, the protocol and GCP guidelines will be strictly followed. Study data will be initially documented as source data in the patient's medical records and study-specific documents by the designated study personnel immediately after each visit. Pseudonymized data, using identifiers such as 'P01' for Lübeck and 'P51' for Augsburg, followed by the corresponding visit number (e.g., P01V2), will be annotated and transferred to a paper-based case report form. Pseudonymized data will also be stored electronically using Microsoft Excel. Standard security measures for using Microsoft Excel will be implemented, including password protection of files, restricted access to authorized personnel only, regular data backups, and storage on secure, access-controlled institutional servers to ensure data confidentiality and integrity. To minimize transcription and transfer errors, a two-step internal monitoring process will be implemented: a second independent study team member will review and verify all data entries on the CRFs against the original source documents, as well as the electronic entries against the paper CRFs. Any discrepancies identified will be resolved promptly through source data verification. All source data will remain at the Institute and CCIM Lübeck. Electronic data may be exchanged between the UKSH, Campus Lübeck, and the UKA Augsburg via secure systems and may be accessed by authorized study personnel for analysis. Image analysis will be carried out at the Department of Dermatology, UKA, Augsburg, Germany. Access to electronic data will be restricted to authorized study personnel only.

9. Termination of the Study

Study participation may be discontinued early in the following cases:

- if treatment failure occurs, defined as no improvement or a worsening of the EASI score at week 16.
- if there is a change in therapy.
- if the participant misses more than 20% of the total treatment duration, corresponding to more than 73 cumulative, non-consecutive days without receiving the study drug.

10. Statistical analysis

Descriptive and inferential statistical analyses will be conducted to evaluate the efficacy of tralokinumab in patients with moderate-to-severe AD over a 52-week period. For the primary endpoint, changes in genital/local patient-reported outcome (PRO) instruments (e.g., Genital-NRS) will be analyzed using paired t-tests or Wilcoxon signed-rank tests, depending on data distribution, to assess within-subject improvement from baseline to week 52. Repeated measures ANOVA or mixed-effects models may be applied to assess longitudinal trends over multiple time points. For the secondary endpoints, similar methods will be used to analyze changes in general PROs (e.g., POEM, ADCT, DLQI, HADS) and clinical severity scores (e.g., EASI, SCORAD, IGA). Missing data will be handled using appropriate imputation methods or sensitivity analyses. For the exploratory imaging analyses, changes in structural and morphological features as measured by confocal microscopy and OCT will be evaluated descriptively and, where possible, compared over time using non-parametric tests or image-derived quantitative metrics. All statistical tests will be two-sided, and a p-value of <0.05 will be considered statistically significant. All questionnaires and clinical scores used in this study, except the newly developed Genital-Investigator Global Assessment (g-IGA), are standardized and validated instruments widely applied in dermatological research and practice. The selection of these instruments was made by [name]. [name] and [name]. [name] in consultation with [name]. [name] to ensure clinical relevance. [name] will also be involved in the data analysis to ensure appropriate interpretation of the results.

11. References

